## **2 Study Conduct**

- Table summarizing the number of participants enrolled by month and by site, by treatment arm.
- Table of study status categories (i.e., completed, death, etc.) by treatment arm.
- Table summarizing weeks from randomization to last clinic visit by treatment arm.

## **3 Baseline Characteristics**

- Table of age, sex, race, and ethnicity by treatment arm.
- Table of Karnofsky performance score and body mass index (BMI) by treatment arm.
- Table of CD4 count and HIV RNA ( $\log_{10}$  copy number and number below lower limit of quantification).
- Table of reason PI-based therapy was needed from eligibility checklist [Q0017-Q0018] (category and specific reason if category=other) by treatment arm.
- Table of AFB smear and mycobacterial culture results by treatment arm.
- Table of RIF and INH drug susceptibility testing (DST) results by treatment arm.
- Table summarizing days from randomization to TB treatment initiation, days from randomization to study-provided ARV treatment initiation, and days from TB treatment initiation to ARV treatment initiation by treatment arm.

## 4 Safety

### 4.1 Grade 3 or Higher Adverse Events

- Table summarizing all grade 3 or higher adverse events within 28 days after study-provided ART and TB treatment initiation that the TDM Team deemed “related to study-provided drug(s)” or “probably related to study-provided drug(s)” or “possibly related to study-provided drug(s)” by treatment arm [*Safety Criterion #1; see section 1.5.2*].
- Table summarizing all new, post-baseline grade 2 or higher signs/symptoms and laboratory toxicities within 28 days after ART initiation from EVW0206 and EVW0207 forms, by type and by treatment arm.
- Table summarizing all grade 3 or higher adverse events beyond 28 days after study-provided ART and TB treatment initiation that the TDM Team deemed “related to study-provided drug(s)” or “probably related to study-provided drug(s)” or “possibly related to study-provided drug(s)” by treatment arm
- Table summarizing all new, post-baseline grade 2 or higher signs/symptoms and laboratory toxicities beyond 28 days after ART initiation from EVW0206 and EVW0207 forms, by type and by treatment arm.

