C	LPV 400 mg/RTV 100 mg tabs BID + two NRTIs + RAL 400 mg BID	INH 300 mg daily, RBT 300 mg daily, then 150 mg daily upon initiation of ART*, EMB (weight-based dose) daily, PZA (weight-based dose) daily, and pyridoxine 25 mg daily. EMB and PZA will be discontinued after 8 weeks of treatment; INH, RBT 150 mg daily (or the adjusted dose determined by PK), and pyridoxine will continue for a minimum total duration of 24 weeks. INH, RBT, and pyridoxine may continue beyond the 24 weeks to a maximum of 48 weeks at the discretion of the primary clinician; the protocol core team must be notified.	LPV/r + two NRTIs + RAL will continue at standard dosing through week 72	This regimen follows the same rationale as for Arm A but adds RAL in an attempt to enhance the antiviral activity of LPV/r when combined with RBT to evaluate whether this approach is associated with a better virologic response than the other two arms.

\*NOTE: In Arms A and C, RBT should be administered at a dose of 300 mg daily until the start of antiretroviral therapy at which time the dose should be reduced to the 150 mg daily dose. If LPV/r is stopped prematurely during TB treatment, the RBT dose should be increased to 300 mg daily and the team should be notified. All participants will receive TB treatment according to in-country TB guidelines for daily TB treatment and directly observed therapy (DOT), except that all study participants will receive daily TB treatment 7 days per week, i.e., participants will not use a 5 days per week schedule that may be recommended in some in-country TB programs.

Accrual will take place in two accrual periods. Accrual period 1 will enroll participants who will undergo an initial dose-finding period before continuing regular study follow-up through 72 weeks. Once review of the dose-finding data in accrual period 1 is completed, accrual period 2 will begin.

#### Accrual Period 1

Sixty participants will be randomized 1:1:1 (20 participants per arm) to one of three treatment arms as detailed above. Anti-TB therapy with study-provided RBT or non-study-provided RIF and non-study-provided INH, EMB, and PZA should be started within 72 hours of randomization. ART should be started as soon as possible after initiating anti-TB therapy, but may be delayed for up to 7-14 days after starting anti-TB therapy to allow participants sufficient time to assess tolerability of TB medications. Participants will then undergo a formal PK and safety evaluation to include:

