### PK and Safety Criteria

- For RBT (Arms A and C), equivalence analyses will compare day  $12 \pm 2$  (after initiation of ART) RBT 24-hour AUC and  $C_{max}$  with control data derived from prior PK studies, as determined by whether the 90% confidence intervals of the ratios of the RBT concentrations (when co-administered with LPV/r) relative to daily RBT concentrations in the absence of LPV/r are fully contained within the pre-specified NEB of 67%-150%. RBT concentrations in Arms A and C will be judged acceptable if equivalence is declared according to these PK parameters.
- For LPV in Arm B, the primary PK parameter is the day  $12 \pm 2$  (after initiation of ART)  $C_{min}$  ( $C_{12}$ ), and the acceptable lower limit value is  $\geq 1$  mg/L. LPV concentrations in Arm B will be judged acceptable if no more than three participants have a  $C_{min} < 1$  mg/L.
- No more than three participants in any treatment arm experience a Grade 3 or Grade 4 AE attributable to study-provided medication by 28 days after ART initiation.
- No more than three participants in any treatment arm discontinue study-provided drug(s) for treatment-limiting toxicity or intolerance (such that PK assessments within the day  $12 \pm 2$  (after initiation of ART) window cannot be completed).

The justification behind the RBT PK criterion is given in section 9.4.1. The other three criteria depend on the number of events (i.e., no more than 3). Based on Table 9.2 below, supposing the underlying rate is 10%, with  $X=3$ , there is an 87% chance of the study regimen in a particular arm going forward to accrual period 2.

Table 9.2. Probability (%) of Deciding the Criterion is Acceptable Based on a Range of Underlying Rates

Underlying Rate	Probability of X or Fewer Events in 20 Participants Given the Underlying Toxicity Rate:				
	X=1	X=2	X=3	X=4	X=5
0.05	0.736	0.925	0.984	0.997	0.999
0.10	0.392	0.677	0.867	0.957	0.989
0.15	0.176	0.405	0.648	0.830	0.933
0.20	0.069	0.206	0.411	0.630	0.804
0.25	0.024	0.091	0.225	0.415	0.617

The core team will also examine the LPV concentrations in Arms A and C in order to determine if RBT affects LPV concentrations. Any dose modifications of

LPV in Arms A and C will be the guided by the modifications proposed for Arm B (see Table 5.1 in section 5.1.1).

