### **1.5.2 Safety Criteria**

- 1) No more than three participants in any treatment arm experience a Grade 3 or Grade 4 AE “related to study-provided drug(s)” (as deemed by the TDM Team: DAIDS Clinical Representative, Protocol Co-Chairs, Protocol Vice Chair, Protocol Pharmacologist, Statisticians, Data Manager, Laboratory Data Manager, and Clinical Trials Specialist) by 28 days after initiation of study-provided ART and TB medications.
- 2) No more than three participants in any treatment arm discontinue study-provided drug(s) for treatment-limiting toxicity or intolerance (such that PK assessments within the day  $12 \pm 2$  [after initiation of study-provided ART and TB medications] window cannot be completed).

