### 4.2 Study Treatment Tolerability

- Table summarizing discontinuations of study-provided drugs within 28 days after study-provided ART and TB treatment initiation by treatment arm [*Safety Criterion #2; see section 1.5.2*].
- Table summarizing discontinuations of study-provided drugs beyond 28 days after study-provided ART and TB treatment initiation by treatment arm.

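### The SAP tables that feed Safety Criteria #1 and #2 run from an undefined start date that does not reproduce the protocol's window and may leave out pre-ART rifabutin events in Arms A and C

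*SAP*

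**What the plan says.** **Protocol.** Section 9.5.1 (PK and Safety Criteria) allows no more than three participants per arm with a Grade 3 or 4 event "attributable to study-provided medication by 28 days after ART initiation". Sections 3.0 and 9.6.1 use the same upper limit, and none of them sets a lower one. The second criterion is no more than three participants per arm who stop study-provided drug for toxicity or intolerance so that the day 12 PK visit cannot be done.

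**SAP 1.5.2.** Criterion #1 keeps the word *by* but changes the anchor: "by 28 days after initiation of study-provided ART and TB medications". Criterion #2 concerns participants who "discontinue study-provided drug(s) for treatment-limiting toxicity or intolerance" such that PK cannot be completed. It has no 28-day window.

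**SAP 4.1 and 4.2.** The tables tagged to the criteria use different wording. For Criterion #1: "Table summarizing all grade 3 or higher adverse events within 28 days after study-provided ART and TB treatment initiation". For Criterion #2: "Table summarizing discontinuations of study-provided drugs within 28 days after study-provided ART and TB treatment initiation by treatment arm". The companion in 4.1 is "Table summarizing all grade 3 or higher adverse events beyond 28 days after study-provided ART and TB treatment initiation", and 4.2 has a matching one for discontinuations. The Grade 2 or higher tables in 4.1 use a third clock, ART initiation alone.

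**The gap.** Protocol section 3.0 has "Anti-TB therapy with study-provided RBT or non-study-provided RIF" begin within 72 hours of randomization. ART follows as soon as possible but may be delayed up to 7-14 days. In Arms A and C the participant takes study-provided rifabutin during that time. Section 5.3.1 lists rifampin among the drugs that the study does not supply, so Arm B takes no study-provided drug before ART. (Section 6.2.2 has a stray phrase calling rifampin study-provided; sections 3.0, 5.1.1 and 5.3.1 agree with each other.)

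**The concern.** *By day 28* is a deadline, and an event before ART meets it. *Within 28 days after* a start date is an interval, and an event before the start lies outside it. With a *within* table and a *beyond* table, neither criterion table covers time before the start.

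That time matters because section 3.0 allows the ART delay so that tolerability of the TB drugs can be assessed. A participant in Arm A or C who stops rifabutin for toxicity in that period and never starts ART is the kind of case Criterion #2 describes. Under a clock that needs both treatments to have begun, this participant has no start date. Only Arms A and C can be affected in this way. SAP section 6 must still report whether the criteria were judged acceptable.

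**Working it through.** **1. What the start date could mean.** The SAP gives no definition.

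- *Later of the two.* SAP 1.3, 1.4 and 1.5.1 use the same anchor for the day 12 PK visit. Protocol 9.5.1 times that visit from ART initiation, and 10.2 describes it as a visit on concomitant TB and HIV therapy. This usage supports the later-of-both reading. Pre-ART events then fall in neither criterion table.
- *First drug.* With a 14-day gap, 28 days from the first drug ends at ART day 28 - 14 = 14. With a 7-day gap it ends at ART day 28 - 7 = 21. Events from then to ART day 28, which the protocol counts, move to the *beyond* table.

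When there is a gap, neither single start date reproduces the protocol's window.

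**2. The plan's own figure.** The rule is at most 3 of 20. For X ~ Binomial(20, p), P(X <= 3) is 0.984, 0.867, 0.648, 0.411 and 0.225 at p = 0.05, 0.10, 0.15, 0.20 and 0.25. This is the X=3 column of Protocol Table 9.2. All 25 cells of the table reproduce, with a largest deviation of 0.0007.

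**3. Upper-range illustration, later-of-both reading.** Let p be the probability of a qualifying event between the first rifabutin dose and ART day 28, and g the gap in days. Assume that every participant has the full gap and that the hazard is constant. The probability that the table counts is

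q = 1 - (1 - p)^(28/(28 + g)).

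At p = 0.20:

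- g = 7: q = 1 - 0.80^(28/35) = 0.1635, a loss of 1 - 0.1635/0.20 = 18%.
- g = 14: q = 1 - 0.80^(28/42) = 0.1382, a loss of 31%.

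Probability of passing, P(X <= 3) with n = 20:

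| Full-window rate p | All events counted | 7-day gap dropped | 14-day gap dropped |
|---|---|---|---|
| 0.10 | 0.867 | 0.927 | 0.957 |
| 0.15 | 0.648 | 0.779 | 0.857 |
| 0.20 | 0.411 | 0.582 | 0.704 |
| 0.25 | 0.225 | 0.387 | 0.529 |

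**4. Smaller effects.**

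- If the pre-ART hazard is half the later hazard, a 14-day gap acts like 0.5 x 14 = 7 days, so the 7-day column applies.
- If 10% have an event after ART starts and a further share has one only in the gap, the table still gives a pass probability of 0.867. Counting every event gives 0.829, 0.787 or 0.648 for a further 1%, 2% or 5%.
- With no qualifying event in the gap, nothing changes.

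The documents give neither the actual gaps nor the event rate in them, so steps 3 and 4 show a range and are not estimates.

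**The case against.** A reader might infer that the SAP starts the clock only once both treatments have begun, that early rifabutin toxicity appears in no table, and that Arms A and C therefore pass too easily. The documents do not support that.

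- **The clock is an inference.** The SAP does not define it. A steady-state PK visit on co-treatment needs both drugs running; a count of adverse events does not.
- **The criterion text is wider than the tables.** SAP 1.5.2 says *by*, and its Criterion #2 has no 28-day limit. The tables cross-refer to 1.5.2, and section 6 judges against 1.5. On that wording, the participant who stops rifabutin and cannot have PK meets Criterion #2.
- **The cases are not invisible.** The diagnosis tables in 4.3 have no ART clock, and 5.1.2 lists rifabutin PK exclusions with reasons. Protocol 9.6.1 includes safety data from participants who leave follow-up before day 28 and counts those lost before then as failures.
- **Other wording pulls the other way.** The Criterion #1 table adds probably and possibly related events, and the Criterion #2 table is not limited to toxicity stops. Both widen the count.
- **The illustration is near a ceiling.** ART is to start as soon as possible, so many gaps may be short. The hazard may also be lower before ART, since Protocol 2.1 says that protease inhibitors markedly raise rifabutin concentrations.
- **No arm can wrongly go forward.** SAP 1.6 states that accrual period 2 will not open.

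These points remove the stronger reading and limit the consequence. They do not remove the mismatch. The 4.1 and 4.2 tables are the ones tagged to the criteria, and they say *within*. The tables in 4.3 and 5.1.2 are not tagged to a safety criterion. Protocol 9.6.1 concerns leaving follow-up, whereas section 6.2.7 encourages participants who stop study drug to stay on study. Wider attribution cannot recover an event outside the window.

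**Conclusion.** The point holds as a mismatch of windows. The tables that supply the counts for Criteria #1 and #2 use an undefined anchor and an interval that matches neither the protocol nor SAP 1.5.2. Neither obvious reading of the anchor restores the protocol's window when ART is delayed.

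Under the later-of-both reading, the omission can only lower the counts in Arms A and C, so it can only favour passing. At a 20% full-window rate the shift runs from nil (no qualifying event in the gap) to 41% against 58% (7 days) or 70% (14 days). The upper figures assume a full gap for everyone and a constant hazard. The net direction across all the wording differences is not established, because the same tables also widen attribution and the types of stop. What is at stake is a possibly wrong criterion judgement in the interim report.

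**What to change.** In SAP 1.5.2, 4.1 and 4.2, use one window: from the first dose of any study-provided drug through 28 days after ART initiation.

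- Under Criterion #2, count any toxicity or intolerance stop that prevents the PK visit, including in participants who never start ART.
- Include those participants' attributed Grade 3 or higher events under Criterion #1.
- Start the *beyond* tables the day after the window closes.
- Show pre-ART events as a separate row, so that the reader can see how many there are and whether they change the judgement.

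The cost is SAP wording and table programming. Protocol 6.2.2 already has drug start dates entered in the database, and SAP section 3 already tabulates the times from randomization to TB treatment and to ART. No new data are needed.

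This restores the protocol's window and changes neither the limit of three participants nor any treatment rule.

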### 6.3 Instructions for Evaluations

All clinical and laboratory information required by this protocol is to be present in the source documents. Sites must refer to the Source Document Guidelines on the DAIDS Web site for information about what must be included in the source document:

<http://www.niaid.nih.gov/labsandresources/resources/daidsclintrsrch/documents/sourcedocappndx.pdf>.

All stated evaluations are to be recorded on the CRF and keyed into the database unless otherwise specified. This includes events that meet the International Conference on Harmonisation (ICH) definitions for a serious adverse event (SAE), regardless of relatedness or association to study medications. Refer to section 11.4.2 for the lists of SAEs and additional events required to be recorded on the CRF and keyed into the database.

To grade diagnoses, signs and symptoms, and laboratory results, sites must refer to the DAIDS Table for Grading the Severity of Adult and Pediatric Adverse Events (DAIDS AE Grading Table), Version 1.0, December 2004 (Clarification, August 2009), which can be found on the DAIDS RSC Web site: <http://rsc.tech-res.com/safetyandpharmacovigilance/>.

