#### Signs and Symptoms

At entry, all grades that occurred within 30 days prior to study entry must be recorded; post-entry, all signs and symptoms  $\geq$  Grade 3 must be recorded. Record all signs and symptoms that led to a change in treatment, regardless of grade.

At entry, all TB-related signs and/or symptoms that occurred within 30 days prior to study entry must be recorded. These include, but are not limited to, fever, weight loss, lymphadenopathy, pulmonary signs and symptoms, and evidence of extrapulmonary disease (e.g., meningitis), presence of wasting, cold abscesses, or abdominal disease.

After entry, resolution of TB-related signs and symptoms reported at entry will be recorded. Any new or resolved Grade  $\geq$  2 TB signs or symptoms reported after entry will be recorded on the CRF.

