#### 6.3.9 Laboratory Evaluations

At screening and entry all protocol required laboratory values must be recorded on the CRFs. For post-entry assessments, record all Grade  $\geq 3$  laboratory values. All laboratory toxicities that led to a change in treatment, regardless of grade, must be recorded.

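### SAP 4.1 tabulates Grade 2 or higher findings by arm, but after entry the protocol requires Grade 2 findings to be recorded only in selected cases, so the Grade 2 counts are not interpretable unless the forms collected all of them

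*SAP*

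**What the plan says.** SAP 4.1 contains two tables with a Grade 2 threshold, both by type and by treatment arm and both drawn from forms EVW0206 and EVW0207. The first is a "Table summarizing all new, post-baseline grade 2 or higher signs/symptoms and laboratory toxicities within 28 days after ART initiation". The second is a "Table summarizing all new, post-baseline grade 2 or higher signs/symptoms and laboratory toxicities beyond 28 days after ART initiation".

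The protocol sets the recording rules after entry:

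- Signs and symptoms (6.3.5): "post-entry, all signs and symptoms $\geq$ Grade 3 must be recorded". There are two additions: "Record all signs and symptoms that led to a change in treatment, regardless of grade", and "Any new or resolved Grade $\geq$ 2 TB signs or symptoms reported after entry will be recorded on the CRF".
- Laboratory values (6.3.9): "For post-entry assessments, record all Grade $\geq 3$ laboratory values". There is one addition: "All laboratory toxicities that led to a change in treatment, regardless of grade, must be recorded".
- All evaluations (6.3): the data to be keyed include "events that meet the International Conference on Harmonisation (ICH) definitions for a serious adverse event (SAE), regardless of relatedness" to study medication.

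The April 2013 clarification memo changes none of these rules. The protocol's own safety endpoint (9.2.3.3.1) counts new Grade 3 or 4 findings that have risen by one grade or more over baseline.

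**The concern.** The SAP promises all new Grade 2 findings, but the protocol does not require all of them to be collected. A Grade 2 nausea or transaminase rise that is managed without changing drugs, and is not serious, need not reach the database. Grade 3 and 4 findings must. A table that mixes the two combines a complete count with a partial one.

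The partial count is also selected. In an open-label trial, whether a Grade 2 finding is recorded depends largely on whether someone changed treatment because of it. That decision can differ between arms when toxicity does not. Gastrointestinal and hepatic tolerability of double-dose lopinavir/ritonavir is the worry raised in protocol section 2.1, and safety and tolerability across the arms is a secondary objective (1.3.4). SAP 1.6 says that Accrual Period 2 will not open, so the 20 participants per arm planned for Accrual Period 1 are the safety data that readers will have. At that size, a few selectively recorded events change an arm's row visibly.

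**Working it through.** **Side-by-side comparison.** The plan gives no figure to reproduce, so the check is textual.

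| Grade 2 finding after entry | Must it be recorded? | Would SAP 4.1 count it? |
|---|---|---|
| Sign or symptom, not TB, treatment unchanged, not serious | No (6.3.5) | Yes |
| Laboratory toxicity, treatment unchanged, not serious | No (6.3.9) | Yes |
| Either kind, led to a treatment change | Yes | Yes |
| TB sign or symptom, new | Yes (6.3.5) | Yes |
| Either kind, part of a serious adverse event | Yes (6.3) | Yes |

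The first two rows are the gap. They are likely to hold the ordinary Grade 2 findings, because protocol 7.1 allows ARVs and TB drugs to continue unchanged at Grade 1 or 2 and leaves management to the investigator. Some drug-specific rules act the other way: 7.2.5 has participants with certain Grade 2 rashes stop rifampin, rifabutin, raltegravir or another suspect drug, and raltegravir is given only in Arm C. Capture can therefore differ by arm, but nothing in the documents says by how much or in which direction.

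**Illustration on assumed inputs.** Only the 20 per arm is from the documents (SAP 1.3). Let *a* be the true proportion with Grade 3 or higher, *b* the true proportion whose worst grade is 2, and *f* the share of the latter with a recorded Grade 2 finding. Then:

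- true Grade 2 or higher rate = a + b
- tabulated rate = a + f × b

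Assume a = 10%, b = 20% to 40%, f = 10% to 50%.

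- Lowest tabulated rate: 0.10 + 0.10 × 0.20 = 0.12, or 2.4 of 20. True rate: 0.10 + 0.20 = 0.30, or 6 of 20.
- Highest tabulated rate: 0.10 + 0.50 × 0.40 = 0.30, or 6 of 20. True rate: 0.10 + 0.40 = 0.50, or 10 of 20.

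For two arms with the same *a* and *b* but different capture, the spurious difference is b × (f₂ − f₁).

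- Capture 10% against 50%: 0.20 × 0.40 = 8 points to 0.40 × 0.40 = 16 points, or 1.6 to 3.2 participants of 20.
- Capture 10% against 25%: 0.20 × 0.15 = 3 points to 0.40 × 0.15 = 6 points, or 0.6 to 1.2 participants of 20.

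Swapping the capture shares between the arms reverses the sign. With f = 1 in every arm, the tabulated rate equals the true rate and the problem disappears.

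**The case against.** **The forms are not supplied.** The protocol states what must be recorded, which is a minimum; sites could enter more. The protocol is Version 1.0 of 2012 with a 2013 memo, and the SAP is dated October 2016. The SAP also uses arrangements absent from the protocol text, such as a TDM Team that judges relatedness. Practice may have changed in documents not available here. This stands: a reader might infer that the Grade 2 counts are certain to be incomplete, and the documents do not support that much. They support incompleteness unless the forms required all Grade 2 findings.

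**Nothing is decided from these tables.** This also stands. They are descriptive, with no planned test. The interim safety criteria in SAP 1.5.2 rest on related Grade 3 or 4 events and on discontinuations. A reader might infer that the interim safety judgement is compromised; it is not.

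**No arm bias is demonstrated.** Correct. A reader might infer that the tables will make a particular arm look worse. The documents give no capture rates, and with 20 per arm the smaller assumed differences are about one participant. SAP 4.1 also does not say that Grade 2 and Grade 3-4 findings will be merged into one rate.

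**Restricting the tables could lose safety data.** This stands against simply deleting the Grade 2 rows. Recorded lower-grade findings should still be shown, and the SAP has IRIS tables but no TB outcome table to which Grade 2 TB signs could be moved.

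None of this removes the mismatch. The SAP gives no reason for a Grade 2 threshold under a section titled for Grade 3 or higher events, and SAP 4.3 uses Grade 3 or higher with the same two forms.

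**Conclusion.** The point holds as a mismatch between what the SAP tabulates and what the protocol requires to be recorded. It affects both Grade 2 tables in SAP 4.1. On the documents supplied, those tables cannot be read as rates of Grade 2 toxicity by arm, because the Grade 2 part depends on treatment changes, TB relatedness, seriousness and voluntary entry.

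The size is unknown. The illustrative 12-30% tabulated against 30-50% true, and the spurious differences of 3 to 16 points in either direction, rest entirely on the assumed rates and capture shares. The conclusion assumes that EVW0206 and EVW0207 followed protocol 6.3.5 and 6.3.9. If they collected every Grade 2 finding, the concern falls away and the SAP need only say so. Grade 3 and 4 counts and the interim safety criteria are unaffected.

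**What to change.** First check what EVW0206 and EVW0207 required of sites after entry. If complete Grade 2 capture is confirmed, keep both tables and state this in SAP 4.1.

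Otherwise:

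1. Make the by-arm summary in both tables new Grade 3 or higher findings that have risen by one grade or more over baseline, in line with protocol 9.2.3.3.1. The baseline is available: the protocol requires signs and symptoms of every grade from the 30 days before entry, and all protocol-required laboratory values at screening and entry.
2. List recorded lower-grade findings separately, labelled as not systematically collected and divided by route: treatment-changing, TB-related, serious adverse event, or voluntarily entered. Keep TB signs and symptoms as their own line in that listing.
3. State that Grade 2 rates will not be compared between arms.

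The cost is a change to SAP table definitions, with no new data. The downside is that the report gives no overall Grade 2 rate by arm.
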